2.2 Secondary Objectives & Endpoints

- 2.2.1** To evaluate the proportion of patients alive and progression free at 24 weeks in the described population.
- 2.2.2** To evaluate the toxicities (according to the NCCN CTCAE v4.03) and tolerability of nivolumab and y-90 in patients with advanced hepatocellular carcinoma
- 2.2.3** To determine the disease control rate (DCR) to the combination of nivolumab and Y-90 at 24 months from the start of nivolumab treatment. DCR is defined as the sum of Complete Response, Partial Response, and Stable Disease (DCR = CR + PR + SD).

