4.4 Toxicity Management: Dose Delays and Discontinuation

Dosing with Yttrium-90 will follow standard of care procedures, and there will be no dose modifications.

Any patient who receives at least one dose of nivolumab will be evaluable for toxicity endpoints. Each patient will be assessed for the development of toxicity by laboratory results and physical exam at each study visit, according to CTCAE 4.03.

Nivolumab may be delayed or discontinued following the instructions detailed in section 4.4.1.

In addition, nivolumab should be discontinued for toxicities as outlined in section 4.4.2.

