6.3 Secondary Endpoints

- For the purposes of this study, patients who have received at least one dose of nivolumab will be considered for evaluation of the safety and toxicity profile of the combination therapy. Safety and tolerability will be measured by the incidence of all adverse events, serious adverse events, deaths and laboratory abnormalities. Adverse event assessments and laboratory tests will be performed at baseline, and continuously throughout the study at the beginning of each subsequent cycle.
- All patients should be re-evaluated for response 21-28 days after Y-90 then every 8 weeks (every 12 weeks after 13 months) using RECIST criteria. Overall response will be calculated by sum of the complete and partial response rates according to measurement of target and non-target lesions as described below.
- Disease control rate will be determined at 24 months from the start of nivolumab treatment by the sum of complete response, partial response and stable response according to measurement of target and non-target lesions as described below.
- Patients who have a response sufficient enough where by shrinkage of the tumors allows them to be considered for transplant will be determined by established BCLC transplant guidelines for individual tumor sizes.
- PFS is defined as the duration of time from start of treatment to time of progression or death, whichever occurs first. Progression assessment will be performed by

investigator each time the patients has a radiologic evaluation after 8 weeks of treatment. OS is defined as the duration of time from start of treatment to time of death.

6.3.1 Definitions:

Evaluable for toxicity. All patients will be evaluable for toxicity from the time of their first treatment with nivolumab.

Evaluable for objective response. Only those patients who have measurable disease present at baseline, have received at least one dose of therapy, and have had their disease re-evaluated will be considered evaluable for response. These patients will have their response classified according to the definitions stated below. RECIST measurements should be used when available. When RECIST measurements cannot be made due to infiltrative disease, evaluable disease needs to be confirmed by pathology.

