7.2.5 Adverse Event Reporting Period

For this study, adverse events will be followed from the time of informed consent until 30 days following the last administration of study treatment. SAE's will also be collected from the time of consent until 100 days following the last administration of study treatment. For patients registered and never treated with study drug, SAE's should be collected for 30 days from the date of consent.

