10.2 Data Analyses Plans

Any subject who has received the investigational combination will be analyzed in an intention to treat format. The MTD will be determined as described in Section 4.3. Objective response rate (ORR = CR + PR) as defined in Section 6.3.3.1 and disease control rate (CR+PR+SD) will be calculated and a 95% confidence interval for response will be obtained using the methods of Porcher and Desseaux (2012) [37]. Progression-free survival will be summarized using the Kaplan-Meier product limit curve. Besides the required reporting of adverse events, adverse events will be summarized for all patients in the trial by type, duration, severity, timing and attribution (probable cause of adverse event). Whole exome sequencing and computational analyses will be performed to assess mutanome and immunome (subpopulations of immune cells). Change in clonal burden landscape of various mutanome and immunome will be analyzed to investigate its correlation with treatment response or development of resistance to treatment.

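### The toxicity set for the Y-90 plus nivolumab regimen is tied to the first nivolumab dose in sections 4.4, 6.3 and 6.3.1, while section 10.2 summarises adverse events for everyone in the trial; one definition is needed

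*Combined protocol and SAP*

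**What the plan says.** Section 2.2.2 sets as a secondary objective the toxicities and "tolerability of nivolumab and y-90 in patients with advanced hepatocellular carcinoma". The regimen starts with Y-90. Nivolumab is planned 7-14 days later and may be delayed to 28 days after Y-90 (section 4.2.2). Patients who cannot start by then come off study and are replaced (sections 4.2.2 and 4.10).

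Three places define the toxicity population by nivolumab:

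- Section 4.4: "Any patient who receives at least one dose of nivolumab will be evaluable for toxicity endpoints".
- Section 6.3, first bullet: "patients who have received at least one dose of nivolumab will be considered for evaluation of the safety and toxicity profile of the combination therapy".
- Section 6.3.1: "All patients will be evaluable for toxicity from the time of their first treatment with nivolumab".

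Section 10.2 points both ways. Its opening sentence reads "Any subject who has received the investigational combination will be analyzed in an intention to treat format". Its adverse-event sentence reads "adverse events will be summarized for all patients in the trial by type, duration, severity, timing and attribution".

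On collection, section 7.2.5 says "adverse events will be followed from the time of informed consent until 30 days following the last administration of study treatment". For registered patients who never receive study drug, however, it asks only for serious adverse events, for 30 days from consent. The schedule in section 5.0 marks adverse-event recording in the Y-90 induction column.

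**The concern.** The objective is about a two-part regimen, but the evaluability rule starts at the second part. Before nivolumab, patients are expected to have recovered from Y-90 side effects to Grade 1 or baseline (section 4.2.2). The clock in section 6.3.1 therefore starts after acute Y-90 toxicity is meant to have settled. Patients whose toxicity does not settle may never start nivolumab, never become evaluable under section 6.3.1, and be replaced. Removal from the set can then depend on the outcome being measured.

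Two analysts working from the same data could produce different safety tables, one following section 6.3.1 and the other the adverse-event sentence of section 10.2. At stake is the reported tolerability of a combination for which section 1.3 says no HCC data exist. No decision rule, sample size or error rate depends on it.

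**Working it through.** No figure stated in the plan rests on these definitions, so there is none to reproduce. The main check is to compare the sections.

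| Section | Y-90-only patients | Events between Y-90 and nivolumab, in patients who start nivolumab |
|---|---|---|
| 4.4 | outside, by implication | not addressed |
| 6.3, first bullet | outside | could be included: it counts all adverse events, assessed from baseline |
| 6.3.1 | outside (never become evaluable) | outside |
| 10.2, opening sentence | outside | not addressed |
| 10.2, adverse-event sentence | inside | inside |
| 7.2.5 | collection rule only, not an analysis set | collection rule only, not an analysis set |

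Two results follow. On who is counted, sections 4.4, 6.3, 6.3.1 and the opening of 10.2 agree with each other and conflict with the adverse-event sentence of 10.2. On when counting starts, section 6.3.1 alone excludes the early period. No passage says which statement governs.

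**How much Y-90 exposure precedes the clock.** Appendix 4, Table 3 gives 0.162 of the activity remaining at 168 hours (day 7). So 1 - 0.162 = 0.838, about 84%, has decayed by the earliest planned nivolumab dose. This is the timing of exposure, not of events.

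**Illustration of the denominator effect.** The inputs are:

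- N = 40 patients given Y-90. This is the target accrual in section 10.1, used here as an assumption about the number treated.
- k = patients who have Y-90 but never nivolumab. This is not in the documents. I use 0, 1 and 2; two is the margin between the 38 patients required and the 40 targeted.
- r = severe-event rate among patients who start nivolumab, assumed to be 20%.
- Every lost patient is assumed to have had a severe event.

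The nivolumab-treated set reports r whatever k is. The rate among all Y-90 patients is [r(N - k) + k]/N.

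- k = 0: (0.20 x 40 + 0)/40 = 8.0/40 = 20%
- k = 1: (0.20 x 39 + 1)/40 = 8.8/40 = 22%
- k = 2: (0.20 x 38 + 2)/40 = 9.6/40 = 24%

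The gap is k(1 - r)/N: 0, 2 and 4 percentage points. With r = 30% the rates are 12.7/40 = 31.8% for k = 1 and 13.4/40 = 33.5% for k = 2.

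The last assumption drives the direction. If neither of two lost patients had a severe event, the all-Y-90 rate would be 0.20 x 38/40 = 7.6/40 = 19%, slightly below the reported 20%.

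Events before nivolumab in patients who do start are a separate omission and remain even at k = 0. The documents do not allow it to be sized. Appendix 1 lists expected effects after TheraSphere (fatigue 29%, fever 25%, nausea 15%, elevated bilirubin 10%) without grade or onset time.

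**The case against.** The strongest reply is that section 10.2 is the analysis plan. It summarises adverse events for everyone, by timing and attribution among other things, which already covers Y-90-only patients and permits a split at the first nivolumab dose. On that reading nothing is lost and the fault is loose wording in section 6.3.1. This stands in part: a planned loss of data cannot be shown. It does not settle the matter, because nothing gives that sentence precedence and the opening sentence of the same section sides with sections 4.4 and 6.3.

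A second reply is that Y-90 is given as institutional standard of care, and that a patient who never had nivolumab did not receive the combination. An as-treated combination set is defensible as one table. As the only set it does not answer objective 2.2.2, which names both components.

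Some stronger readings are tempting and are not supported:

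- A reader might infer that section 7.2.5 contradicts section 6.3.1. It is a collection window, so it shows only that events are gathered which section 6.3.1 leaves out.
- A reader might infer that all three sections exclude early events in patients who start nivolumab. Only section 6.3.1 does.
- A reader might infer that the data for a full safety set are certain to exist. If study drug in section 7.2.5 means nivolumab, as the wording of section 4.1 suggests, non-serious events in Y-90-only patients may not be fully collected.
- A reader might take a large bias as established. The documents give no Y-90-only rate. Section 4.10 covers stopping for any reason, and a persistent Grade 2 effect could also prevent a start, so treating every loss as a severe event gives the upper end for a given k.

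**Conclusion.** The concern holds as a conflict between definitions that can bias reported toxicity downward if section 6.3.1 is followed. It is not a demonstrated bias. The denominator effect is zero if every Y-90 patient starts nivolumab. It is 2 to 4 points (20% reported against 22-24%) if 1 or 2 of 40 are lost, assuming a 20% severe-event rate among starters and a severe event in each lost patient. The omission of pre-nivolumab events in starters cannot be sized from the documents.

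The point is limited to the secondary safety summary. Section 4.3.1 already counts a toxicity delay of more than 2 weeks in starting nivolumab as a DLT, but that serves the MTD and not objective 2.2.2. Collection of serious adverse events and the two-stage response design are unaffected. The change should be made, since the wording is easily aligned and the excluded patients may be the least tolerant ones.

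**What to change.** In sections 4.4, 6.3, 6.3.1 and 10.2, use one definition: the safety set is every patient who received Y-90 on study, with adverse events counted from Y-90.

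In section 10.2:

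- Tabulate adverse events from Y-90 to first nivolumab, from first nivolumab onward, and overall.
- Report Y-90-only patients separately, with their number and the reasons they did not start nivolumab.
- Keep patients with at least one nivolumab dose as a second table.
- Reword the opening sentence so that it no longer competes with the safety set.

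In section 7.2.5, state whether study drug includes Y-90, and provide for collection of all adverse events, not only serious ones, in Y-90-only patients over a period the sponsor sets.

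The cost is wording in five sections, one table split, possibly a little more adverse-event recording for Y-90-only patients, and perhaps a slightly less favourable reported toxicity rate. No DLT, replacement or dosing rule changes.

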6.3.2 Disease Parameters

Measurable disease. Measurable lesions are defined as those that can be accurately measured in at least one dimension (longest diameter to be recorded) as ≥ 20 mm (≥ 2 cm) by chest x-ray or as ≥ 10 mm (≥ 1 cm) with CT scan, MRI, or calipers by clinical exam. All tumor measurements must be recorded in millimeters (or decimal fractions of centimeters).

Malignant lymph nodes. To be considered pathologically enlarged and measurable, a lymph node must be ≥ 15 mm (≥ 1.5 cm) in short axis when assessed by CT scan (CT scan slice thickness recommended to be no greater than 5 mm [0.5 cm]). At baseline and in follow-up, only the short axis will be measured and followed.

Non-measurable disease. All other lesions (or sites of disease), including small lesions (longest diameter < 10 mm [< 1 cm] or pathological lymph nodes with ≥ 10 to < 15 mm [≥ 1 to < 1.5 cm] short axis), are considered non-measurable disease. Bone lesions, leptomeningeal disease, ascites, pleural/pericardial effusions, lymphangitis cutis/pulmonitis, inflammatory breast disease, and abdominal masses (not followed by CT or MRI), are considered as non-measurable.

Note: Cystic lesions that meet the criteria for radiographically defined simple cysts should not be considered as malignant lesions (neither measurable nor non-measurable) since they are, by definition, simple cysts.

'Cystic lesions' thought to represent cystic metastases can be considered as measurable lesions, if they meet the definition of measurability described above. However, if non-cystic lesions are present in the same patient, these are preferred for selection as target lesions.

Target lesions. All measurable lesions up to a maximum of 2 lesions per organ and 5 lesions in total, representative of all involved organs, should be identified as target lesions and recorded and measured at baseline. Target lesions should be selected on the basis of their size (lesions with the longest diameter), be representative of all involved organs, but in addition should be those that lend

themselves to reproducible repeated measurements. It may be the case that, on occasion, the largest lesion does not lend itself to reproducible measurement in which circumstance the next largest lesion which can be measured reproducibly should be selected. A sum of the diameters (longest for non-nodal lesions, short axis for nodal lesions) for all target lesions will be calculated and reported as the baseline sum diameters. If lymph nodes are to be included in the sum, then only the short axis is added into the sum. The baseline sum diameters will be used as reference to further characterize any objective tumor regression in the measurable dimension of the disease.

Non-target lesions. All other lesions (or sites of disease) including any measurable lesions over and above the 5 target lesions should be identified as non-target lesions and should also be recorded at baseline. Measurements of these lesions are not required, but the presence, absence, or in rare cases unequivocal progression of each should be noted throughout follow-up.

6.3.3 Response criteria

6.3.3.1 Evaluation of target lesions

Complete Response (CR): Disappearance of all target lesions. Any pathological lymph nodes (whether target or non-target) must have reduction in short axis to <10mm.

Partial Response (PR): At least a 30% decrease in the sum of the diameters of target lesions, taking as reference the baseline sum diameters.

Progressive Disease (PD): At least a 20% increase in the sum of the diameters of target lesions, taking as reference the smallest sum on study (this includes the baseline sum if that is the smallest on study). In addition to the relative increase of 20%, the sum must also demonstrate an absolute increase of at least 5 mm (0.5 cm). (Note: the appearance of one or more new lesions is also considered progressions).

Stable Disease (SD): Neither sufficient shrinkage to qualify for PR nor sufficient increase to qualify for PD, taking as reference the smallest sum diameters while on study.

6.3.3.2 Evaluation of Non-Target Lesions

Complete Response (CR): Disappearance of all non-target lesions and normalization of tumor marker level. All lymph nodes must be non-pathological in size (<10 mm [<1 cm] short axis).

Non-CR/Non-PD: Persistence of one or more non-target lesion(s) and/or maintenance of tumor marker level above the normal limits.

Progressive Disease (PD): Appearance of one or more new lesions and/or unequivocal progression of existing non-target lesions. Unequivocal progression should not normally trump target lesion status. It must be representative of overall disease status change, not a single lesion increase.

Although a clear progression of “non-target” lesions only is exceptional, the opinion of the treating physician should prevail in such circumstances, and the progression status should be confirmed at a later time by the review panel (or Principal Investigator).

6.3.3.3 Evaluation of best overall response

The best overall response is the best response recorded from the start of the treatment until disease progression/recurrence (taking as reference for progressive disease the smallest measurements recorded since the treatment started). The patient's best response assignment will depend on the achievement of both measurement and confirmation criteria.

Responses will be assessed using CT scans or magnetic resonance imaging according to standard RECIST 1.1 criteria in order to assess disease progression. These criteria will also allow for patients who experience an initial disease flare, and as some patients who will have a delayed response may experience an initial disease flare, we will allow patients to continue receiving nivolumab beyond progression (see section 4.2.5)

6.3.3.4 Duration of Response

Duration of overall response: The duration of overall response is measured from the time measurement criteria are met for CR or PR (whichever is first recorded) until the first date that recurrent or progressive disease is objectively documented (taking as reference for progressive disease the smallest measurements recorded since the treatment started).

The duration of overall CR is measured from the time measurement criteria are first met category when no lesions can be measured is not advised for CR until the first date that progressive disease is objectively documented.

Duration of stable disease: Stable disease is measured from the start of the treatment until the criteria for progression are met, taking as reference the smallest measurements recorded since the treatment started, including the baseline measurements.

7.0 ADVERSE EVENTS

This study will be conducted in compliance with the Data Safety Monitoring Plan (DSMP) of the Robert H. Lurie Comprehensive Cancer Center of Northwestern University (please refer to NOTIS for additional information). The level of risk attributed to this study requires High Intensity Monitoring as outlined in the DSMP. In addition, the study will abide by all safety reporting regulations, as set forth in the Code of Federal Regulations.

7.1 Adverse Event Monitoring

Adverse event data collection and reporting, which are required as part of every clinical trial, are done to ensure the safety of subjects enrolled in the studies as well as those who will enroll in future studies using similar agents. Adverse events are reported in a routine manner at scheduled times during a trial (see Section 5 and 7.2.5 for time points). In addition, certain adverse events must be reported in an expedited manner to allow for optimal monitoring and patient safety and care.

All patients experiencing an adverse event, regardless of its relationship to study drug, will be followed until:

- the adverse event resolves or the symptoms or signs that constitute the adverse event return to baseline;
- any abnormal laboratory values have returned to baseline;
- there is a satisfactory explanation other than the study drug for the changes observed; or
- death.

7.2 Definitions & Descriptions

7.2.1 Adverse Event

An **adverse event** (AE) is any symptom, sign, illness or experience that develops or worsens in severity during the course of the study. Intercurrent illnesses or injuries should be regarded as adverse events. Abnormal results of diagnostic procedures are considered to be adverse events if the abnormality:

- results in study withdrawal
- is associated with a serious adverse event
- is associated with clinical signs or symptoms
- leads to additional treatment or to further diagnostic tests
- is considered by the investigator to be of clinical significance

Recording of AEs should be done in a concise manner using standard, acceptable medical terms. In general, AEs are not procedures or measurements, but should reflect the reason for the procedure or the diagnosis based on the abnormal measurement. Preexisting conditions that worsen in severity or frequency during the study should also be recorded (a preexisting condition that does not worsen is not an AE). Further, a procedure or surgery is not an AE; rather, the event leading to the procedure or surgery is considered an AE.

If a specific medical diagnosis has been made, that diagnosis or syndrome should be recorded as the AE whenever possible. However, a complete description of the signs, symptoms and investigations which led to the diagnosis should be provided. For example, if clinically significant elevations of liver function tests are known to be secondary to hepatitis, "hepatitis" and not "elevated liver function tests" should be recorded. If the cause is not known, the abnormal test or finding should be recorded as an AE, using appropriate medical terminology (e/g/ thrombocytopenia, peripheral edema, QT prolongation).

7.2.2 Severity of AEs

All adverse events will be graded according to the NCI Common Terminology Criteria for Adverse Events (CTCAE) version 4.03. The CTCAE v4.03 is available at <http://ctep.cancer.gov/reporting/ctc.html>

If no CTCAE grading is available, the severity of an AE is graded as follows:

- Mild (grade 1): the event causes discomfort without disruption of normal daily activities.
- Moderate (grade 2): the event causes discomfort that affects normal daily activities.
- Severe (grade 3): the event makes the patient unable to perform normal daily activities or significantly affects his/her clinical status.
- Life-threatening (grade 4): the patient was at risk of death at the time of the event.
- Fatal (grade 5): the event caused death.

